### 7.3.7 Immediate Post-Procedure Medical Therapy

Post-procedure loading with clopidogrel is suggested.

Protamine sulfate should be given for anticoagulation reversal only when clinically indicated (e.g., femoral oozing).

Prescribe appropriate endocarditis prophylaxis for 6 months following device implantation. The decision to continue endocarditis prophylaxis beyond 6 months is at physician discretion.

### 7.3.8 Anticoagulation/antiplatelet Therapy

If the post-procedure TEE demonstrates adequate seal (residual leak  $\leq 5$  mm) and there is no evidence of thrombus, subjects should receive DAPT (ASA 75-100 mg QD and clopidogrel 75 mg QD) until 45 days post-procedure. NOTE: A substitute P2Y12 inhibitor (i.e., prasugrel, ticagrelor) may be used in known non-responders to clopidogrel.

If the 45-day TEE demonstrates adequate closure, DAPT should be continued to 6 months. For high bleeding risk (HBR) subjects, monotherapy (ASA preferred, P2Y12 inhibitor permitted) may be initiated per physician judgment.

If a 6-month TEE demonstrates adequate closure, DAPT should be replaced by monotherapy (ASA preferred, P2Y12 inhibitor permitted) to 12 months post-procedure.

Beginning 12 months post-procedure, medical therapy should be administered per standard of care.

- **Inadequate seal:** Subjects with inadequate seal (residual leak >5 mm) at the post-procedure TEE (or any subsequent TEE) should be evaluated for treatment with OAC and ASA for 4-6 weeks followed by TEE. If inadequate seal persists, anti-thrombotic therapy should be individualized for the patient, balancing bleeding risk with the associated persistent inadequate seal (seen on TEE).
- **Thrombus:** Subjects with thrombus detected on the device at the post-procedure TEE (or any subsequent TEE) should be evaluated for treatment with OAC and ASA for 4-6 weeks followed by TEE. Anti-thrombotic therapy should be individualized for the patient, balancing bleeding risk and the assumed thrombo-embolic risk associated with the TEE findings.

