Antiplatelet and Anticoagulant Therapy	
Antiplatelet and oral anticoagulant therapy requirements are as follows:
 
Pre-Procedure
 
The following should be administered prior to the index procedure:
 
 
• ASA 81-100 mg (administered prior to procedure and continued daily)
 
 
Intra-Procedure
 
Intraprocedural medication should be administered per standard of care, maintaining an activated clotting time (ACT) of 250-350s throughout the procedure.
 
Post-Procedure
 
If the post-procedure TEE demonstrates adequate seal (residual leak <math>\leq 5</math> mm) and there is no evidence of thrombus, subjects should receive DAPT (ASA 75-100 mg QD and clopidogrel 75 mg QD) until 45 days post-procedure.
 
If the 45-day TEE demonstrates adequate closure, DAPT should be continued to 6 months. For high bleeding risk (HBR) subjects, monotherapy (ASA preferred, P2Y12 permitted) may be initiated per physician judgement.
 
If the 6-month TEE demonstrates adequate closure, DAPT should be replaced by monotherapy (ASA preferred, P2Y12 permitted).
 
 
• Inadequate seal: Subjects with inadequate seal (residual leak <math>>5</math> mm) at the post-procedure TEE (or any subsequent TEE) should be evaluated for
 

	
treatment with NOAC and ASA for 4-6 weeks followed by TEE. If inadequate seal persist, anti-thrombotic therapy should be individualized for the patient balancing bleeding risk with the associated persistent inadequate seal (seen on TEE).
 
 
• Thrombus: For thrombus detected on the device at the post-procedure TEE (or any subsequent TEE) should be evaluated for treatment with OAC and ASA for 4-6 weeks followed by TEE. Anti-thrombotic therapy should be individualized for the patient, balancing bleeding risk and the assumed thrombo-embolic risk associated with the TEE findings.
 

Patient Population	
Patients presenting with non-valvular atrial fibrillation who are at increased risk for stroke and systemic embolism based on CHA2DS2-VASc scores, and who are recommended for oral anticoagulation therapy but have an appropriate rationale to seek a non-pharmacologic alternative to oral anticoagulation.

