**CHA2DS2-VASc Score**

A clinical risk stratification scheme for predicting stroke and thromboembolism in patients with nonvalvular AF, updated from the earlier CHADS2 score. Patients are assigned a score from 0 to 9 by adding the points for each applicable risk factor below to obtain a total score:

Risk Factors	Score
Congestive Heart Failure	1
Hypertension	1
Age $\geq 75$ years	2
Diabetes mellitus	1
Stroke/TIA/thromboembolic event in the past	2
Vascular disease (prior MI, PAD, or aortic plaque)	1
Age 65 to 74 years	1
Sex category (female gender)	1

Closure success	Device success (see definition) followed by successful LAA closure (complete closure or peri-device residual leak $\leq 5$ mm in width on TEE at 45 days post-procedure). NOTE: The primary protocol definition of closure success is at the primary performance endpoint evaluation time point of 45 days; closure success at 6 and 12 months will also be evaluated.
CNS hemorrhage	NeuroARC defined  as any brain, spinal cord, or retinal hemorrhage on the basis of imaging or pathology, not caused by trauma (includes symptomatic intracerebral hemorrhage [Type 1.b], symptomatic subarachnoid hemorrhage [Type 1.c], and covert CNS hemorrhage [Type 2.b])
CNS infarction	NeuroARC defined  as any brain, spinal cord, or retinal infarction on the basis of imaging, pathology, or clinical symptoms persisting for $\geq 24$ h (includes ischemic stroke [Type 1.a], ischemic stroke with hemorrhagic conversion [Type 1.a.H], stroke not otherwise specified [Type 1.d], symptomatic hypoxic-ischemic injury [Type 1.e], covert CNS infarction [Type 2.a], and covert CNS infarction with hemorrhagic conversion [Type 2.a.H])
Composite efficacy	Freedom from the composite of all-cause mortality, all stroke, TIA, and systemic thromboembolism

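### The 6-month step-down to monotherapy depends on closure alone, and the thrombus rule covers only the device, so off-device intracardiac thrombus meets only a step-down instruction

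*Combined protocol and SAP*

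**What the plan says.** Section 7.3.8 of Version B, and the antithrombotic therapy row of the synopsis (Section 3.0), set out a sequence of steps, each triggered by a TEE.

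- **After the procedure.** DAPT to 45 days needs two findings: a residual leak of 5 mm or less, "and there is no evidence of thrombus, subjects should receive DAPT". The thrombus condition has no limit on location.
- **45 days.** "If the 45-day TEE demonstrates adequate closure, DAPT should be continued to 6 months". Monotherapy is optional for subjects at high bleeding risk. Thrombus is not mentioned.
- **6 months.** "If a 6-month TEE demonstrates adequate closure, DAPT should be replaced by monotherapy (ASA preferred, P2Y12 inhibitor permitted) to 12 months post-procedure". The synopsis has the same trigger: "If the 6-month TEE demonstrates adequate closure, DAPT should be replaced by monotherapy". Again thrombus is not mentioned.
- **12 months on.** "Beginning 12 months post-procedure, medical therapy should be administered per standard of care".

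Two exception bullets follow. One covers a leak above 5 mm. The other covers thrombus: "Subjects with thrombus detected on the device at the post-procedure TEE (or any subsequent TEE) should be evaluated for treatment with OAC and ASA". The synopsis carries the same limit: "For thrombus detected on the device at the post-procedure TEE (or any subsequent TEE) should be evaluated for treatment with OAC and ASA".

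**The concern.** The first step treats seal and absence of thrombus as separate requirements. The 45-day and 6-month steps keep only the closure requirement and leave thrombus to the exception bullet, which reaches only thrombus on the device. Thrombus elsewhere in the heart, seen with a small leak, therefore falls between the two.

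At 6 months the written rule then points in the unsafe direction, because it reduces antithrombotic therapy with thrombus present. If the text were followed literally, the outcomes that could be affected are the secondary embolic events and major safety events after that TEE.

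**Working it through.** There is no figure in the plan to reproduce, and no sample-size or event-rate calculation bears on the point. The check is to lay the rules of 7.3.8 out as a table and look for text elsewhere that fills the cell in question.

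**Step 1: what closure means.** Section 7.3.8 does not define adequate closure. Section 5.3.2, Section 5.3.3.2.3 and the Closure success entry in Appendix A all define closure on TEE by leak width. The Appendix A entry begins "Device success (see definition) followed by successful LAA closure (complete closure or peri-device residual leak" and gives the 5 mm limit; none of the three has a thrombus condition. The first step of 7.3.8 lists seal and thrombus as two conditions, so adequate seal does not by itself imply no thrombus.

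**Step 2: the 6-month TEE, subject still on DAPT.**

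| Finding | Instruction in 7.3.8 that fits |
|---|---|
| Leak above 5 mm | Inadequate-seal bullet: evaluate for OAC and ASA, then repeat TEE |
| Leak 5 mm or less, no thrombus | Step down to monotherapy |
| Leak 5 mm or less, thrombus on the device | Thrombus bullet, alongside the step-down sentence |
| Leak 5 mm or less, intracardiac thrombus off the device | Step-down to monotherapy only |

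**Step 3: the last row at the other TEEs.**

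- *Post-procedure:* no sentence applies, because DAPT requires no thrombus and the bullet requires thrombus on the device. This is silence rather than a wrong instruction, and it is remote. The TEE is done before tether release (Section 7.4), after echocardiography has confirmed that no echocardiographic exclusion is met (Section 7.3.4). Those exclusions include intracardiac thrombus (Section 6.2.2.2.2).
- *45 days:* DAPT continues, with monotherapy optional at high bleeding risk.
- *12 months:* standard of care applies, so the step-down sentence has no role.

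**Step 4: whether another section fills the cell.**

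- Section 7.9 ties closure success to absence of thrombus, but only for the optional cardiac CT at 12 months.
- Section 6.7 foresees deviations to protect a subject. It is a general clause, not a rule for this finding.
- The adverse event sections allow a new thrombus to be reported and medication to be started for it. They do not say which antithrombotic therapy to use.

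None of these gives an antithrombotic rule for off-device thrombus at 6 months.

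**The case against.** The strongest reply is that the gap depends on a narrow reading. Adequate closure is undefined in 7.3.8, and taking its meaning from an endpoint definition is an inference. The first step excludes thrombus at any site, so its natural complement is the thrombus bullet, and the reference to the device may be loose drafting. The bullet's closing sentence individualizes therapy according to the TEE findings, and the 12-month CT note shows that thrombus was not meant to be ignored. In addition, the rules say what should be done, not what must be done, and a physician who sees thrombus would probably anticoagulate.

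Much of this stands as a limit on impact. It does not supply the missing rule. The individualizing sentence belongs to the bullet for thrombus on the device, the CT note governs one optional scan at 12 months, and probable intent is a reason to correct the wording.

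A reader might infer more than the text supports:

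- *That thrombus is ignored at 45 days and 6 months.* It is not. Thrombus on the device is covered at every TEE.
- *That every implanted subject is exposed to the step-down.* The 6-month sentence replaces DAPT, so it does not literally address a subject already on OAC or monotherapy.
- *That no other provision in the protocol would let a physician act.* Section 6.7 and the adverse event provisions leave room to act. The claim is only that no other antithrombotic rule in 7.3.8 fits.
- *That the trial's size yields an expected number of cases.* A threshold derived from 20 subjects would hold for any event and would say nothing about this one. Moreover, 20 is a ceiling on enrollment, and the 6-month TEE applies only to subjects with an implant.

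**Conclusion.** The gap is real but narrow. It concerns a subject still on DAPT at the 6-month TEE, with a leak of 5 mm or less and intracardiac thrombus off the device. For that subject the only matching antithrombotic instruction in 7.3.8 is to step down. The 45-day omission is milder, because its default is to continue DAPT.

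The conclusion assumes that adequate closure means leak width, as in the closure definitions. The practical effect is small, on the judgment that the case is rare and that physicians would probably not step down with thrombus in view. Harm would also require an event that other therapy would have prevented. No endpoint definition is affected, and the analysis is descriptive with no hypothesis testing. The documents give no rate for off-device thrombus, so none is claimed.

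This is a minor point: a cheap improvement for patient safety, worth making because a stated rule points the wrong way.

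**What to change.** Make two wording changes, in both Section 7.3.8 and the synopsis:

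1. Change the scope of the thrombus bullet to *intracardiac thrombus, on the device or elsewhere*. This matches the term in exclusion 6.2.2.2.2 and also fills the post-procedure silence. Limiting it to the left atrium would leave thrombus elsewhere in the heart without a rule once change 2 is made.
2. Add *and there is no evidence of thrombus* to the 45-day and 6-month sentences, so that they match the first step. This also removes the overlap at 6 months, where thrombus on the device currently meets both the step-down sentence and the bullet.

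The bullet asks only that the subject be evaluated for treatment, so the choice of therapy stays with the clinical team. The cost is a small wording amendment, approved as Section 14.5 requires. It could travel with the next amendment. Endpoints, data collection and sample size are unchanged. The same wording should carry into the pivotal trial that this study is meant to inform (Section 4.3).

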## 7.4 TEE Post Implant

A confirmatory TEE will be conducted after the implant is delivered, prior to tether release. The investigator will confirm the findings of the ICE imaging: position and seal.

## 7.5 Pre-discharge Follow-up

Post-procedure assessment must occur during the index procedure hospitalization prior to hospital discharge, and must include:

- Physical examination
- TTE
- Stroke assessment, to include:
  - Questionnaire for Verifying Stroke-Free Status (QVSFS)
  - NIH Stroke Scale (NIHSS); the NIHSS must be performed by a neurologist or NIHSS-certified research staff
  - Patients in whom a neurologic event is suspected on the basis of the QVSFS, NIHSS, or other signs or symptoms will require a neurologic examination and evaluation performed by a neurologist or clinical designee (e.g., neurology fellow). In patients with confirmed stroke, mRS must be documented, and repeated 90 ± 14 days post-event to assess disability.
- Current concomitant medications documentation. If DAPT has been interrupted or terminated the stop date (and resumption date, if applicable) and the reason for interruption/termination should be recorded.

Prior to hospital discharge, research staff should review the follow-up requirements with the subject to ensure compliance with the subsequent follow-up assessment:

- For subjects discharged from the index procedure hospitalization on or before day 6 post-procedure, telephone numbers should be obtained from the subject to ensure the ability to reach him or her for the required 7 + 2-day telephone contact. These phone numbers should

include all home numbers, work numbers and primary physician numbers. A phone number of a relative or friend should also be requested.

- For subjects discharged from the index procedure hospitalization on day 7 or later post-procedure, telephone numbers should be obtained from the subject to ensure that the subject returns to the clinic for the 45-day follow-up assessment.

## 7.6 7-day Follow-up (Telephone Contact / Optional Clinic Visit)

All subjects must undergo a follow-up assessment on day 7 to 9 post-procedure to enable timely documentation of safety endpoint events.

If the subject has not yet been discharged from the index procedure hospitalization at day 7 post-procedure, the 7-day follow-up may be conducted in-hospital, and no separate telephone contact is necessary.

For subjects who have already been discharged from the index procedure hospitalization, the 7-day follow-up will be conducted via telephone contact.

The 7-day follow-up assessment must include:

- Questionnaire for Verifying Stroke Free Status (QVSFS). If any question is answered "Yes", a formal neurologic examination and evaluation must be performed by a board-certified neurologist or clinical designee (e.g., neurology fellow).
- Current concomitant medications documentation. If DAPT has been interrupted or terminated the stop date (and resumption date, if applicable) and the reason for interruption/termination should be recorded.
- Documentation of any adverse events occurring since the previous evaluation.

Note: for subjects discharged from the index procedure hospitalization prior to day 7, but who return to the clinic as part of their regular medical care during the specified follow-up window (7 to 9 days post procedure), the 7-day follow-up assessment may be conducted during the clinic visit, and no separate telephone contact is necessary.

## 7.7 45-day Follow-up (Clinic Visit)

All subjects will return to the clinic at 45 days ( $\pm$  7 days) post-procedure for a clinical evaluation. The 45-day follow up visit will include the following assessments:

- Physical examination
- Stroke assessment, to include:
  - Questionnaire for Verifying Stroke Free Status (QVSFS)
  - NIH Stroke Scale (NIHSS); the NIHSS must be performed by a neurologist or NIHSS-certified research staff
  - Patients in whom a neurologic event is suspected on the basis of the QVSFS, NIHSS, or other signs or symptoms will require a neurologic examination and evaluation performed by a neurologist or clinical designee (e.g., neurology fellow). In patients with confirmed stroke, NIHSS and mRS must be documented, and repeated  $90 \pm 14$  days post-event.

- A transesophageal echocardiogram (TEE) must be performed in all subjects who left the index procedure with an implanted CLAAS device.
- Current concomitant medications documentation. If DAPT has been interrupted or terminated the stop date (and resumption date, if applicable) and the reason for interruption/termination should be recorded.
- Documentation of any adverse events occurring since the previous evaluation.

Prior to concluding the visit, research staff should also review the follow-up requirements with the subject to help ensure that the patient returns to the clinic for the 6-month follow-up visit.

## 7.8 Six-month Follow-up (Clinic Visit)

All subjects who received a CLAAS implant will return to the clinic at 6 months ( $\pm$  30 days) to include the following assessments:

- Physical examination
- Stroke assessment, to include:
  - Questionnaire for Verifying Stroke Free Status (QVSFS)
  - NIH Stroke Scale (NIHSS); the NIHSS must be performed by a neurologist or NIHSS-certified research staff
  - Patients in whom a neurologic event is suspected on the basis of the QVSFS, NIHSS, or other signs or symptoms will require a neurologic examination and evaluation performed by a neurologist or clinical designee (e.g., neurology fellow). In patients with confirmed stroke, NIHSS and mRS must be documented, and repeated  $90 \pm 14$  days post-event.
- A transesophageal echocardiogram (TEE).
- Current concomitant medications documentation. If DAPT has been interrupted or terminated the stop date (and resumption date, if applicable) and the reason for interruption/termination should be recorded. If monotherapy has been initiated due to high bleeding risk, the factors contributing to the high bleeding risk assessment should be documented.
- Documentation of any adverse events occurring since the previous evaluation.

Prior to concluding the visit, research staff should also review the follow-up requirements with the subject to help ensure that the patient returns to the clinic for the 12-month follow-up visit

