### 3.0 Protocol Synopsis

Study Title	
The Conformal Prague Study
 
An evaluation of the safety and performance of the Conformal Left Atrial Appendage Seal for Left Atrial Appendage Occlusion

Study Device	
The Conformal Left Atrial Appendage Seal (CLAAS®) is a permanent implant designed to occlude the left atrial appendage (LAA) to eliminate blood flow into and clot passage from the LAA.
 
Intended Use	
The CLAAS system is intended to reduce the risk of thromboembolism from the left atrial appendage in patients with non-valvular atrial fibrillation who:
 
 
• Are at increased risk for stroke and systemic embolism based on CHA2DS2-VASc scores and are recommended for oral anticoagulation (OAC) therapy; AND
 
• Have an appropriate rationale to seek a non-pharmacological alternative to OAC, taking into account the safety and effectiveness of the device compared to OAC.
 

Objective	
The primary objective is to evaluate the safety and technical performance of the CLAAS system for closure of the left atrial appendage in patients with non-valvular atrial fibrillation at increased risk for stroke and systemic embolism who are recommended for oral anticoagulation (OAC) therapy but have an appropriate rationale to seek a non-pharmacological alternative to OAC.

Study Design	A prospective, single center, open-label, single arm, study to evaluate the safety and technical performance of the CLAAS system for closure of the left atrial appendage. Patients presenting with non-valvular atrial fibrillation who are at increased risk for stroke and systemic embolism based on CHA 2 DS 2 -VASc scores, and who are recommended for oral anticoagulation therapy but have an appropriate rationale to seek a non-pharmacologic alternative to oral anticoagulation, and who meet all eligibility criteria, will be enrolled in the study and undergo LAA closure with the CLAAS system.
Sample Size	Up to 20 subjects shall be enrolled in the study.
Investigational Sites	One (1) investigational site in Europe.
Study Duration / Follow-up Period	Subjects will have clinical follow-up prior to hospital discharge and at 7 days, 45 days and, 6 and 12 months. Transesophageal echocardiographic (TEE) follow-up will be performed at 45 days and, 6 and 12 months.

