## 5.0 Study Design

### 5.1 Study Design Overview

This prospective, single center, open-label, single arm, study will enroll up to 20 subjects aimed at examining the safety and technical performance of the CLAAS device for LAA closure. Patients with non-valvular atrial fibrillation who are at increased risk for stroke and systemic embolism based on CHA2DS2-VASc scores, and who are recommended for oral anticoagulation therapy but have an appropriate rationale to seek a non-pharmacologic alternative to oral anticoagulation, and who meet all eligibility criteria, will be enrolled in the study and undergo LAA closure with the CLAAS system.

Subjects will have clinical follow-up prior to hospital discharge and at 7 days, 45 days, and 6- and 12-months post procedure. Transesophageal echocardiographic (TEE) follow-up will be performed at 45 days and, 6 and 12 months in all subjects.

The primary safety endpoint is freedom from major adverse events, evaluated at hospital discharge or at 7 days post-procedure (whichever occurs later), and defined as absence of the composite of all-cause mortality, ischemic stroke, systemic thromboembolism, and device- or procedure-related adverse events requiring open cardiac surgery or major endovascular intervention. The primary performance endpoint is closure success, defined as device success followed by successful LAA closure (complete closure or peri-device residual leak ≤5 mm in width on TEE at 45 days post-procedure). The study will also report additional secondary safety, performance, and effectiveness endpoints, as well as using TEE to confirm post-procedure ICE evaluation of device seal and position as a comparator for device success.

All endpoints will be reported using appropriate descriptive statistics in the primary analysis population (the ITT population), and no hypothesis testing will be performed. As a secondary analysis, all endpoints will be evaluated in the Implanted Patient (IP) population.

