## 7.0 Study Procedures and Assessments

### 7.1 Schedule of Procedures and Assessments

Table 3. Study Schedule of Procedures and Assessments

	Screening	Index Procedure (day 0)	Pre-discharge 	7 Days (+2 days) 	45 days (45 ± 7 days)	6 months (± 30 days)	12 months (± 30 days)
	Clinic Visit	Clinic Visit	Clinic Visit	Telephone Contact / Optional Clinic Visit	Clinic Visit	Clinic Visit	Clinic Visit
Demographics and Medical History	●						
Review of General Eligibility Criteria	●						
Informed consent	●						
Physical Examination	●		●		●		●
Stroke Assessment	●		●	●	●	●	●
CHA2DS2-VASc; HAS-BLED scores	●						
Pregnancy Test	●						
Laboratory tests	●						
12-lead ECG	●						
Brain Imaging	●		●				
TTE			●				
TEE	● 	● 			●	●	●
ICE		● 					
Angiography		●					
LAA occluder implantation		●					
Concomitant Medications	●	●	●	●	●	●	●
Adverse events	● 	●	●	●	●	●	●

 The pre-discharge visit must be conducted prior to hospital discharge from the index procedure; patients discharged on day 6 or earlier must also be followed up via telephone contact at 7 (+2) days post-procedure. For subjects who have not been discharged before day 7, the 7-day assessment may be performed in the clinic and no separate telephone contact is necessary.

 In patients who have been discharged from the index procedure hospitalization on day 6 or earlier, a telephone contact must be conducted at 7 (+2) days post procedure, and must include ascertainment of

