## 7.9 Twelve-month Follow-up (Clinic Visit)

All subjects who received a CLAAS implant will return to the clinic at 12 months ( $\pm$  30 days) post-procedure for additional follow-up, to include the following assessments:

- Physical examination
- Stroke assessment, to include:
  - Questionnaire for Verifying Stroke Free Status (QVSFS)

- NIH Stroke Scale (NIHSS); the NIHSS must be performed by a neurologist or NIHSS-certified research staff
- Patients in whom a neurologic event is suspected on the basis of the QVSFS, NIHSS, or other signs or symptoms will require a neurologic examination and evaluation performed by a neurologist or clinical designee (e.g., neurology fellow). In patients with confirmed stroke, NIHSS and mRS must be documented, and repeated  $90 \pm 14$  days post-event.
- A transesophageal echocardiogram (TEE) or Cardiac CT Scan\*
- Current concomitant medications documentation. If DAPT has been interrupted or terminated the stop date (and resumption date, if applicable) and the reason for interruption/termination should be recorded. If monotherapy has been initiated due to high bleeding risk, the factors contributing to the high bleeding risk assessment should be documented.
- Documentation of any adverse events occurring since the previous evaluation.

\*NOTE: Subjects evaluated by Cardiac CT which on review are found to have complete seal without thrombus will be considered as having closure success. If review indicates incomplete seal or thrombus, further evaluation by TEE will be required.

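### Late safety endpoints are analysed by ITT, but the 6- and 12-month visits are scheduled only for implanted subjects; and closure success does not carry one definition across 45 days, 6 months and 12 months

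*Combined protocol and SAP*

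**What the plan says.** All references are to protocol Version B, the current text.

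**Follow-up.** Section 10.2.1 defines ITT by introduction of the Access Sheath, whatever treatment followed, and makes it primary for every secondary endpoint. Under 5.3.3, secondary endpoints without their own time point are evaluated up to 6 and 12 months. Major safety events, mortality and embolic events fall under that rule; major procedure-related complications are in-hospital only.

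The overview in 5.1 says "Subjects will have clinical follow-up prior to hospital discharge and at 7 days, 45 days, and 6- and 12-months post procedure" and "Transesophageal echocardiographic (TEE) follow-up will be performed at 45 days and, 6 and 12 months in all subjects". The synopsis agrees on clinical follow-up: "Subjects will have clinical follow-up prior to hospital discharge and at 7 days, 45 days and, 6 and 12 months". Section 7.7 says "All subjects will return to the clinic at 45 days" and then limits only the imaging: "A transesophageal echocardiogram (TEE) must be performed in all subjects who left the index procedure with an implanted CLAAS device". Sections 7.8 and 7.9 limit the visit itself: "All subjects who received a CLAAS implant will return to the clinic at 6 months" and "All subjects who received a CLAAS implant will return to the clinic at 12 months". Section 6.6.3 names a final assessment for implanted subjects only. Section 8.8.1 collects adverse events from enrollment to study closure, and 10.3.3 makes no adjustment for missing data.

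**Closure success.** At 45 days (5.3.2) it means device success and then complete closure or a residual leak of at most 5 mm on TEE. At 6 months (5.3.3.2.3 and the synopsis) the same name has only the leak criterion. Appendix A defines the term with device success and TEE at 45 days, and adds in a note that it will also be evaluated at 6 and 12 months. The CT note in 7.9 grants closure success at 12 months on complete seal without thrombus and does not mention device success.

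**The concern.** A subject who is enrolled but leaves the laboratory without an implant stays in the ITT denominator to 12 months. Under 7.8 and 7.9 that subject has no visit after day 45, and those visits are where stroke screening and adverse-event documentation take place. Late safety results labelled ITT could then rest on implanted subjects plus whatever others report unprompted.

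For closure, a rate under one name at three time points will be read as a course over time. Part of any change could come from the definition. Section 4.3 says the study is to inform a pivotal trial, so both the late safety rate and the closure trend are likely to be carried forward.

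**Working it through.** The plan states no rate, precision target or power to reproduce. Its only figure here is the target of 20 subjects (10.1). The counts k and m below are assumptions.

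**Part 1: who is seen late**

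| Section | 45 days | 6 and 12 months |
|---|---|---|
| 5.1, synopsis (clinical follow-up) | no implant limit | no implant limit |
| 7.7 | all subjects; TEE if implanted | – |
| 7.8, 7.9 | – | implanted subjects only |
| 10.2.1 with 5.3.3 (analysis) | ITT | ITT |

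Let k be the number of enrolled subjects who leave without an implant.

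- Share of ITT with no scheduled late contact = k/20: 0% for k = 0, 5% for k = 1, 10% for k = 2, 15% for k = 3.
- If each subject has an assumed chance p of leaving without an implant, the chance of at least one among 20 is 1 − (1 − p)^20: 33% for p = 2%, 64% for 5%, 88% for 10%, 96% for 15%.
- With no late event among the 20 − k subjects seen, the exact two-sided 95% upper bound is 1 − 0.025^(1/(20 − k)): 16.8% for 20 seen, 17.6% for 19, 18.5% for 18, 19.5% for 17.
- At the extreme, if every unseen subject had an event, the ITT rate would be k/20: 5%, 10% or 15% for k = 1, 2 or 3.

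The loss of precision is small. What matters is whether the stated population was observed.

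**Part 2: what counts as closure**

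Let m be the number of implanted subjects without device success whose TEE leak is at most 5 mm by day 45 and does not change afterwards. Assume all other implanted subjects have device success and stay sealed, and count non-implanted subjects as not successful.

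- 45 days (5.3.2), ITT: (20 − k − m)/20
- 6 months (5.3.3.2.3), ITT: (20 − k)/20
- 12 months, device success required: (20 − k − m)/20
- 12 months, CT note applied to all m subjects, each with complete seal and no thrombus: (20 − k)/20

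| k | m | 45 days | 6 months | 12 months, device success required | 12 months, CT note |
|---|---|---|---|---|---|
| 0 | 0 | 100% | 100% | 100% | 100% |
| 0 | 1 | 19/20 = 95% | 20/20 = 100% | 95% | 100% |
| 0 | 2 | 18/20 = 90% | 20/20 = 100% | 90% | 100% |
| 1 | 1 | 18/20 = 90% | 19/20 = 95% | 90% | 95% |

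Each such subject adds 1/20 = 5 points between 45 days and 6 months. The IP analysis does not remove this: for k = 1 and m = 1 it gives 18/19 = 94.7% at 45 days and 19/19 = 100% at 6 months.

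**The case against.** **Section 5.1 is an overview.** Its statement on TEE in all subjects is already narrowed by 7.7, while 6.6.3, 7.8 and 7.9 agree with one another, so limiting late visits to implanted subjects may be the intention. That is possible. It would settle the schedule, but the ITT label in 10.2.1 would then not fit the late safety endpoints. Table 3 does not help, because it does not say who attends.

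**Adverse events are collected to study closure, without an implant limit.** This stands. A reader might infer that late events in non-implanted subjects fall outside the study or are certain to be lost; 8.8.1 does not support that. What is missing is a scheduled contact. The 5-year telephone contact mentioned there is not in Table 3.

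**Unseen subjects need not be counted as event-free.** A reader might infer that 0/19 observed would be reported as 0/20. No section says so. Section 10.3.1 reports binary variables with sample size, and 10.3.3 makes no adjustment for missing data and summarises loss to follow-up, which is at least as consistent with 0/19.

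**The 6-month endpoint may be meant as anatomical seal.** This also stands. A reader might infer that Appendix A requires device success at every time point, or that 12 months has a single definition. The entry ties its criterion to 45 days and reaches later visits only through a note, and the CT note is an affirmative rule without device success. The text does not settle which was meant.

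**Affected closure subjects may not occur.** Section 7.3.8 provides for a post-procedure TEE leak above 5 mm, but device success is judged on ICE, and 7.4 adds a TEE check of seal before tether release. Neither rules out such a subject, and neither gives a rate.

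The separate SAP promised in 10.3.1, not among these documents, and the planned listings could settle or show denominators. They cannot create a visit.

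**Conclusion.** Two mismatches in the text hold and should be fixed. First, the late safety endpoints are assigned to ITT while 7.8 and 7.9 schedule late visits for implanted subjects only, against 5.1 and the synopsis. This is a risk of under-ascertainment in 5% of the ITT set per non-implanted subject. Second, closure success does not mean the same thing at 45 days and 6 months, and at 12 months the result depends on whether Appendix A or the CT note is applied; each affected subject shifts the rate by 5 points.

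Confidence is high on the wording and limited on the size. The documents give no implant-failure or device-success rate, and both effects are zero if all 20 subjects are implanted with device success. Both primary endpoints are unaffected. The study is descriptive, so no error rate or power is involved.

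**What to change.** 1. Reconcile 5.1, the synopsis, 6.6.3, 7.8 and 7.9 on whether non-implanted subjects are followed to 12 months. Then either obtain vital status, stroke screening and adverse events for them at 6 and 12 months, for example by telephone, or label the 6- and 12-month safety results as IP. In both cases report observed n/N.
2. Use one definition of closure success at 45 days, 6 and 12 months, and state in the CT note whether device success applies. If a seal-only measure is wanted at 6 and 12 months, give it a different name.
3. Report closure over ITT, with non-implanted subjects counted as not successful, and over IP, each with n/N.

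The cost is wording, possibly a few telephone calls, and perhaps a slightly lower late closure figure.
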